Emotion Prosthetics for Augmentation of Mindfulness: Protocol

May 7 2018

Contents

- 1. Study Description 2
 - 1.1 Objective: 2
 - 1.2 Specific Aims 2
 - Aim 1: 2
 - Aim 2: 2
 - Aim 3: 2
 - 1.3 Background 3
 - 1.4 Significance 4
- 2. Research Activities 4
 - 2.1 Location 4
 - 2.2 Assessment Days 4
 - 2.3 Consent 4
 - 2.4 Interviews 4
 - 2.5 Self-report Measures 5
 - 2.6 Tasks 5
 - OUTLINE of procedures during the tasks 5
 - All of tasks will be video recorded 5
 - Physiological measurements during tasks 6
 - A) Calibrations: 6
 - B) Interventions: 6
 - C) Cognitive and affective tasks: 6
 - 2.7 REGARDING INCOMPLETE DATA COLLECTION 7
- 3. PERSONNEL 7

1. Study Description

1.1 Objective:

This protocol will examine and elucidate a mechanistic model for tuned vibroacoustic stimulation (TVS), an exteroceptive cue that has been shown to reduce subjective and physiological indicators of stress and increase behavioral performance, applied to mindfulness meditation for stress reduction and emotion regulation in healthy adults.

1.2 Specific Aims

Aim 1: Examine how TVS added to brief instructed mindfulness meditation can affect psychological state and performance. This aim is to show that TVS is particularly potent as a catalyst towards the types of experiences documented in experienced meditators.

Hypothesis 1.1: Positive affect and calmness: TVS added to mindfulness will increase subjective positive affect and calmness compared with mindfulness alone, particularly in individuals whose state is not strongly affected by mindfulness alone.

Hypothesis 1.2: Heightened states of awareness: TVS added to mindfulness will heighten state of awareness compared with mindfulness alone and particularly in individuals whose state is not strongly affected by mindfulness alone.

Hypothesis 1.3: Performance: TVS added to mindfulness will improve performance on visual attentional preference and empathy tasks and particularly in individuals whose state is not strongly affected by mindfulness alone and in individuals with increased positive affect and heightened state of awareness.

Aim 2: Examine how TVS added to brief instructed mindfulness meditation can affect physiological indicators of emotion regulation. Our overall hypothesis is that TVS, in combination with some other task, increases performance on that task by increasing emotion regulation. Mindfulness meditation is one such task that, without TVS may decrease emotion regulation in some people - TVS will counter that.

Hypothesis 2.1: TVS added to mindfulness increases physiological indicators of emotion regulation, including decreased galvanic skin response (GSR; index of sympathetic reactivity), increased heart rate variability (HRV; index of parasympathetic reactivity), and increased prefrontal gamma and theta band EEG compared with mindfulness alone during the intervention and follow-up tasks.

1.3 Background

For the past decade, prospective studies have shown that positive emotions have been correlated with physical health and longevity (Chida & Steptoe, 2008). Those who experience more positive emotions have fewer colds, reduced inflammation, and can recover from stress more effectively (Cohen, Alper, Doyle, Treanor, & Turner, 2006; Ong, Bergeman, Bisconti, & Wallace, 2006; Steptoe, O'Donnell, Badrick, Kumari, & Marmot, 2008). According to the Fredrickson's broaden and build theory, positive emotion such as joy, interest, love and contentment can broaden an individual's thought-action repertoire and build on that individual's personal resources, which should lead to an upward spiral of positive emotion that can counter downward spirals of negativity and stress (Fredrickson, 2004; Fredrickson & Joiner, 2002; Tugade & Fredrickson, 2004). Induction of positive emotion has been shown to broaden scope of attention using a global-local visual processing task, increase breadth of thought-action repertoire using a thought listing task, and result in faster recovery from cardiovascular sequelae of negative emotions (Fredrickson & Branigan, 2005; Fredrickson & Levenson, 1998). Perceived positive social connections increase positive emotions, an effect moderated in part by baseline vagal tone (Kok et al., 2013).

Mindfulness interventions also have physical and mental health benefits. Mindfulness can be defined as moment-to-moment awareness in one's present experience and adopting an attitude of openness or acceptance toward one's experience (Creswell, 2017). Standard protocol for Mindfulness-Based Stress Reduction (MBSR) consists of 8 weekly 2.5-hour group sessions and has been applied to many populations including those with depression and anxiety (Kabat-Zinn, 1982; Kabat-Zinn et al., 1992; Ludwig & Kabat-Zinn, 2008; Teasdale et al., 2000). There are also brief experimental mindful attention inductions that have been developed although these approaches appear to have small and transient effects (Schofield, Creswell, & Denson, 2015; Westbrook et al., 2013). Positive predictors of mindfulness include individuals with higher self-esteem, autonomy and competence. Negative predictors of mindfulness include individuals with higher levels of neuroticism trait, anxiety, depression, and negative affectivity (Brown & Ryan, 2003). However, studies have also shown that mindfulness is less effective when individuals behave compulsively or automatically, without awareness or attention to one's behavior (Brown & Ryan, 2003).

Prior research has shown that mindfulness do affect markers of calmness and stress, including heart rate variability (HRV), galvanic skin response (HRV), and EEG (Azam, Katz, Mohabir, & Ritvo, 2016; Lomas, Ivtzan, & Fu, 2015). Stress is characterized by hyper-reactivity in the sympathetic nervous system which is associated with increased arousal and vigilance, and compromised reactivity of the parasympathetic nervous system, which helps to regulate emotion and stress responses (Kibler, Tursich, Ma, Malcolm, & Greenberg, 2014; Lehrer & Gevirtz, 2014). HRV is widely used as a biomarker for the coordinated activity of the sympathetic and parasympathetic nervous symptom. A calmer, less stressful state is typically marked by increased HRV, likely attributed to respiration based parasympathetic stimulation (Grossman & Taylor, 2007). GSR is also a reliable index for sweat gland activity and changes in activation level of the sympathetic nervous system, and GSR usually increases with higher levels of stress (Mohan, Sharma, &

Bijlani, 2011). EEG changes, such as elevated prefrontal gamma and theta, have also been associated with state of relaxed alertness.

Large scientific literature supports the role of vibration in regulating physiology (Takahashi, Ohashi, & Yokoyama, 2011; M. Uchikune, 2002; M. Uchikune, 2004). Based on literature, slow whole-body vibration, in the 0.01 to 0.3 Hz range, is associated with increased ratings of pleasantness and increased parasympathetic tone (M. Uchikune, 2002; M. Uchikune, 2004). Stimulation at about 100 Hz has been shown to activate the posterior insula (Coghill et al., 1994) which is associated with increased attention to interoception, as promoted in many meditative traditions. Transcutaneous targets for the vibration frequencies have also been identified, including stellate ganglion and vagus nerve (Cipriano et al., 2014; Fang et al., 2016). Currently, in [name] lab, TVS has been shown to reduce subjective stress, increase positive affect, along with increases in behavioral performance ([name]). We hypothesize that TVS added to mindfulness will increase positive emotions and heighten state of awareness, leading to broadening of perspectives in individuals.

1.4 Significance

In this study, we will be testing the potential for TVS combined with mindfulness meditation to be used to increase well-being (subjective calmness, heightened states of awareness, increased preference and physiological reactivity) in a healthy population. Positive results would suggest that dynamic intervention is possible without effort, medications, or psychotherapy. This would be the first such intervention

2. Research Activities

2.1 Location

All procedures will occur at the PI's lab, [name]

2.2 Assessment Days

The study takes place in one assessment day lasting up to 4 hours

2.3 Consent

Participants will have the study initially described to them by the clinician at the Oxford Building, and if the participant agrees to participate, they will sign informed consent.

2.4 Interviews

Participants will undergo several structured diagnostic interviews including a post-intervention debriefing:

1. Mini-International Neuropsychiatric Interview (MINI 7.0): The MINI 7.0 is a short, structured clinical diagnostic interview designed for DSM-V that covers all psychiatric disorders. It is widely used in epidemiological studies and multi-site clinical trials (Sheehan et al., 1998).
2. North American Adult Reading Test (Uttl, 2002)

3. Post intervention Questionnaire: Determine how individuals felt about the study overall, whether it was consistent with the individual's overall expectation of the experiment, and whether improvements could be made.

All or some of these interviews will be audio or video recorded. The videos may be reviewed by study personnel and investigators for quality assurance, training purposes, or analysis. Physical backups are kept in locked filing cabinets and are labeled with subject identification number and date only. Electronic video or audio files will be stored on a password protected server which only study personnel can access. Video and audio recordings will be kept indefinitely and may later be reviewed by other researchers. Participants may request destruction of video or audio recordings, or may also request not to be audio or video taped.

2.5 Self-report Measures

--Pre-task

- 1) Demographic and screening questionnaire
- 2) Mindfulness attention awareness scale (Carlson & Brown, 2005)
- 3) Patient Health Questionnaire (Kroenke, Spitzer, & Williams, 2001)
- 4) Meditation experience questionnaire
- 5) Drug history questionnaire (Ventegodt & Merrick, 2003)
- 6) modified Differential Emotion Scale (Fredrickson, Tugade, Waugh, & Larkin, 2003)

--During tasks

- 1) Positive and Negative Affect Schedule (Watson, Clark, & Tellegen, 1988) will be given initially, and then after each intervention (meditation vs. meditation + TVS). This will also be given after the completion of each task (Mind in the Eyes, Global Local Task)

--Post-tasks

- 1) 5-Dimensional Altered State of Consciousness rating scale(Dittrich, 1998)

2.6 Tasks

OUTLINE of procedures during the tasks

--Calibration (EEG, Pupil/Eye tracking, baseline GSR/EKG, vibration)

--Intervention 1: Meditation*

--Tasks 1: Global-Local Test, Mind in the Eyes

--Intervention 2: Meditation and TVS*

--Tasks 2: Global-Local Test, Mind in the Eyes

*Participant will be randomized whether they get meditation first or meditation and TVS first

All of tasks will be video recorded (calibration, intervention, tasks). The videos may be reviewed by study personnel and investigators for quality assurance, training purposes, or analysis. Physical backups are kept in locked filing cabinets and are labeled with subject identification number and date only. Electronic video or audio files will be stored on a password protected server which only study personnel

can access. Video and audio recordings will be kept indefinitely and may later be reviewed by other researchers. Participants may request destruction of video or audio recordings, or may also request not to be audio or video taped.

Physiological measurements during tasks include galvanic skin response (GSR) measured using electrodes placed on the index and middle finger, pupillary dilation indices, EKG (electrocardiography) which will be measured using three electrodes (left clavicle, right clavicle, and under the right rib), respiration (using a respiration belt), and EEG (mobile EEG monitor on head) will be collected during: 1) calibrations, 2) interventions and 3) cognitive and affective tasks. All of the stated physiological measurements will be collected except pupillary dilation indices will not be collected during interventions (meditation, meditation + TVS) because participants are encouraged to relax and are given the opportunity to close their eyes during those times.

A) Calibrations:

Calibration tasks will initially be completed for physiology collection including a vibration calibration that allows assessment of individualized vibration frequency preferences, a GSR/EKG calibration at baseline, EEG calibration at baseline and pupillary dilation calibration. During the EEG calibration, there are some images that may evoke negative emotions, which is in the introduction, and participants are encouraged to stop the calibration at any time if they feel uncomfortable with the images.

B) Interventions:

Participants will undergo 2 blocks (randomized for order). 1) guided mindfulness meditation and 2) guided mindfulness meditation with TVS (0.1 Hz to 100 Hz) using SubPac, which is a marketed, wearable vibration technology that can deliver TVS, worn like a backpack. Participants will be wearing the SubPac (vest with vibration) the whole time but only during mindfulness with meditation, will the vest vibrate at various frequencies. The intensity of stimuli can vary from barely detectable through somewhat uncomfortable, but will not be painful. Similar vibratory stimuli have been standardly used in [name]'s lab. The intensity of the vibration will be adjusted to the subjects' comfort. Each of the interventions will be have a 12 minuted guided mindfulness meditation, with or without vibration coming out of the vest. They are given the choice to either sit in a desk chair or in a lounge chair, both in the same room. We advise them to concentrate to the meditation and the feelings in their body.

C) Cognitive and affective tasks:

These tasks are standard for our emotion/cognitive research lab.

1. Global-local visual processing task (Fredrickson & Branigan, 2005)

-- In general, images contain both local and global features. This task determines which attention is first directed, either at the local features (details, parts) or global features (the whole)

-- There will be a letter "T" made up of 4 smaller letter "T's". The smaller T's and the large "T" are incongruent in its orientation. The global feature of the letter "T" (the whole) will be of a particular orientation (up, down, left, right) and the local features (details, parts, in this case the 4 smaller letter "T's") will be of a different orientation (up, down, left, right). Participants will have to choose an answer by looking at the letter "T". There is no right answer, and the participant has the choose between 1) a letter "T" with congruent 4 smaller "T's" in the orientation of the global features (the whole) or 2) A letter "T" with congruent 4 smaller "T's" in the orientation of the local features (details, parts).

2. Reading the Mind in the Eyes test (Baron-Cohen, Wheelwright, Hill, Raste, & Plumb, 2001)

Participants will see a picture of a person only with the eyes present. There will be four words that describes the possible mood of the participant. The participant will be asked to choose the adjective that fits best with eye mood conveyed by picture of the person when only the eyes can be observed.

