### **Canonical Analysis Strategy**

Our canonical strategy for all aims in which outcome measures (e.g., physiology) are examined preintervention and post-intervention will as follows:

**Quality Control:** Data will be inspected visually and using our lab's standard algorithms to eliminate subjects, blocks, and trials in which data do not appear to be representative of the obtained measure, e.g., for EEG, data are eliminated when >3 channels have outlying means, standard deviations, are interpolated, or have unacceptably high levels of impedance.

**Preprocessing:** Data will be preprocessed using our lab's standard procedures which are consistent with industry standard procedures, e.g., via guidelines for psychophysiology from the Society for Psychophysiological Research. Outliers will be rescaled via windsorization.

**Data Reduction:** if more than one outcome measure of a given type (e.g., electrodes, for EEG) are employed, principal components analysis (PCA) will be used to yield aggregate indices across proposed outcome variables.

**Analysis:** Pre-intervention index values will be interacted with intervention type (mindfulness alone vs. TVS added to mindfulness) to explain variance in post-intervention index values using hierarchical regression; in the absence of an interaction, preintervention values will be regressed from post-intervention values before using intervention type as an independent variable to explain variance in post-intervention values in a residual regression analysis. The change in R^2 will be used as an effect size. Type I error will be controlled across the number of examined factors. Each type of outcome listed separately below will be interpreted as a statistically separate family for control of familywise error.

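### Only Tasks 1 is listed between the two blocks and the plan expects a TVS effect in those tasks, yet the SAP neither defines the block 2 pre-value nor looks for carryover

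*Protocol*

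**What the plan says.** Protocol 2.6 gives the sequence as calibration, first intervention, "Tasks 1: Global-Local Test, Mind in the Eyes", second intervention, then the same two tasks again. A footnote adds: "Participant will be randomized whether they get meditation first or meditation and TVS first". Nothing else is listed between the blocks. On length, section 2.6 states: "Each of the interventions will be have a 12 minuted guided mindfulness meditation, with or without vibration coming out of the vest". Section 2.2 puts everything on one day: "The study takes place in one assessment day lasting up to 4 hours".

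In section 1.2, Hypothesis 2.1 predicts the physiological benefit of TVS "compared with mindfulness alone during the intervention and follow-up tasks", and Hypothesis 1.3 predicts better task performance after TVS. SAP outcomes 4, 5, 6, 8, 11 and 12 are all measured in those tasks.

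The SAP's Canonical Analysis Strategy reads: "Pre-intervention index values will be interacted with intervention type (mindfulness alone vs. TVS added to mindfulness" (the bracket closes after the last word), to explain the post-intervention value. If there is no interaction, a residual regression on the pre-intervention value follows. Order, sequence, period, washout and carryover are not mentioned.

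Two kinds of baseline data exist. Protocol 2.6 has one physiological calibration, done at the start. Protocol 2.5 gives the PANAS at the start and after each intervention, and says of the tasks: "This will also be given after the completion of each task". A PANAS value shortly before block 2 will therefore exist. The SAP does not say whether it serves as a pre-value.

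**The concern.** The tasks have two roles that pull against each other. They are where the plan looks for a continuing effect of TVS, and they are the only listed separation between the blocks. If the effect has gone by the time of the tasks, the task-based outcomes have little to detect. If it has not, participants given TVS first may begin mindfulness alone with some TVS effect still present.

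Randomising the order balances time effects such as fatigue or practice. It does not remove carryover that is larger after TVS than after mindfulness alone, and neither does a period term. Both primary outcomes, positive affect and HRV during meditation, are compared across the two blocks. Either contrast could be distorted without any planned analysis showing it. The direction of the distortion depends on a choice that the SAP leaves open.

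**Working it through.** The documents give no sample size, effect size, SD or alpha level, so there is no figure of the plan to reproduce. The carryover fractions, correlations, n, alpha and 1:1 allocation of the two orders below are assumptions.

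**Step 1: session-start pre-value.** Let τ be the TVS effect, π the effect of being in block 2, and Lτ the carryover of TVS into block 2 beyond any carryover of mindfulness alone.

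- Block 1, TVS minus mindfulness alone: τ - 0 = τ.
- Block 2, TVS minus mindfulness alone: (τ + π) - (Lτ + π) = τ(1 - L).
- Average: [τ + τ(1 - L)]/2 = τ(1 - L/2).

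The block effect π cancels and L does not. A session-start value is the same for both blocks of one person, so adjusting for it does not alter this result. The contrast is 87.5%, 75%, 62.5% and 50% of τ for L = 0.25, 0.5, 0.75 and 1. A simulation of the SAP's residual regression (200,000 participants, τ = 0.5 SD, within-person correlation 0.6) gave 75% at L = 0.5 and 50% at L = 1, in agreement.

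**Step 2: block-start pre-value.** Let L0 be the carryover when the block 2 pre-value is taken, L1 the carryover when the outcome is taken, and b the slope on the pre-value. Half of the mindfulness-alone records are from block 2 of TVS-first participants, so the mean pre-value under mindfulness alone is raised by L0τ/2. Adjustment adds b × L0τ/2 back to the contrast:

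contrast/τ = 1 - (L1 - b × L0)/2.

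With b = 0.6, against the same simulation:

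| L0 | L1 | Formula | Simulated residual regression / ANCOVA |
|---|---|---|---|
| 0.5 | 0.5 | 1 - (0.5 - 0.3)/2 = 90% | 90% / 90% |
| 1 | 1 | 1 - (1 - 0.6)/2 = 80% | 79% / 80% |
| 0.5 | 0.25 | 1 - (0.25 - 0.3)/2 = 102.5% | 102% / 103% |
| 0.5 | 0 | 1 - (0 - 0.3)/2 = 115% | 114% / 115% |

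Steady carryover still shrinks the contrast, but by less. Carryover that fades between the pre-value and the outcome can leave no bias or inflate the contrast.

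**Step 3: which case applies.** For HRV, the only resting baseline listed is the initial calibration, so step 1 is the likelier case. For positive affect, both a session-start and a pre-block-2 PANAS exist, so either step could apply.

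**Step 4: precision of block 1 alone.** Block 1 precedes any carryover; the same simulation returned 99 to 100% of τ from it. Take n = 40 (20 per order), a paired effect of 0.5 SD of the within-person difference, two-sided alpha 0.05 and within-person correlation ρ. After baseline adjustment the standardised effect is 0.5 × √(2(1 - ρ))/√(1 - ρ²) = 0.5 × √(2/(1 + ρ)). That is 0.598 at ρ = 0.4 and 0.527 at ρ = 0.8. Multiplying by √(20/2) gives noncentrality 1.89 and 1.67, and the noncentral t on 37 degrees of freedom gives power of about 45% and 37%.

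**The case against.** Four stronger readings are tempting, and the documents support none of them.

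- **That carryover is built into the design.** Hypothesis 2.1 reaches only as far as the follow-up tasks. To bias a primary outcome, the effect must also last through a second 12-minute guided meditation for HRV, or to its end for PANAS. Nothing states this, and neither task duration nor decay of the effect is given. Protocol 1.3 describes the effects of brief mindfulness inductions as small and short-lived, though it says this of mindfulness, not TVS. The outline may also be incomplete: it omits the PANAS administrations, and the interviews have no stated timing. A missing rest line does not prove that there is no rest.
- **That the bias is toward zero for both primary outcomes.** This needs carryover in the direction of benefit, larger than that of mindfulness alone, and not offset by the pre-value. Step 2 shows that it can fail, and for PANAS the direction is open.
- **That a specific loss of power can be quoted for this trial.** Such figures depend on the assumed n. For an unadjusted paired test at two-sided 0.05 with a paired effect of 0.5 SD, L = 0.5 takes power from 56% to 36% at n = 20, but only from 99% to 91% at n = 80.
- **That a null result could never be told apart from carryover.** Data that bear on the question will be collected. What is missing is a pre-specified analysis of them, although the block 1 comparison would often be too weak to settle the matter.

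What stands is narrower: the separation relied on is the period in which the plan expects an effect, and the SAP neither defines the block 2 pre-value nor examines order.

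**Conclusion.** The concern holds as a gap in the analysis plan, not as proof of bias. Carryover of TVS into a second mindfulness-alone block is plausible on the plan's own hypotheses and of unknown size. If a session-start pre-value is used, the expected contrast is (1 - L/2) of the true effect. This assumes equal allocation to the two orders and takes L as net carryover. If a block-start pre-value is used, the patterns examined gave about 79% to 115% of the true effect, at an assumed correlation of 0.6. The trial remains interpretable. The SAP should be amended because the change is cheap and the direction of any bias currently depends on an undefined choice.

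**What to change.** Add to the SAP, for both primary outcomes:

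1. State that the session-start value (initial PANAS, baseline HRV) is the pre-value for both blocks, or justify another choice, and include period (order) and participant terms. A random participant effect keeps the session-start covariate estimable. These terms deal with time effects and pairing; they do not remove carryover.
2. Pre-specify a supportive comparison of TVS-first with mindfulness-first in block 1 only, adjusted for the initial PANAS or baseline HRV.
3. Describe by order the PANAS collected after the first set of tasks and the HRV recorded during those tasks. This indicates what effect remains shortly before block 2. It is not proof of carryover during block 2.

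Report items 2 and 3 beside the crossover estimate and use neither to choose the primary analysis.

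The cost is SAP wording and two small analyses of data already planned, with no change to the session. The drawback is the low precision of item 2, about 37% to 45% power under the assumptions in the working, so it can support the main result but cannot decide it.

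### The EEG calibration may contaminate the pre-intervention values: its images may evoke negative emotions, the calibration order is given in two ways, and the SAP has no period term

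*Protocol*

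**What the plan says.** Protocol section 2.6 places calibration once, at the start of the session: "Calibration tasks will initially be completed for physiology collection". On the EEG part it says "During the EEG calibration, there are some images that may evoke negative emotions", and that "participants are encouraged to stop the calibration at any time if they feel uncomfortable with the images".

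The section lists the calibration components in two orders. The outline reads "Calibration (EEG, Pupil/Eye tracking, baseline GSR/EKG, vibration". The text under A) Calibrations names vibration first and then "a GSR/EKG calibration at baseline, EEG calibration at baseline and pupillary dilation calibration". Neither list is declared to be the running order. No recovery step is listed between calibration and Intervention 1, and no new baseline is described before Intervention 2.

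Section 2.5 gives the PANAS at the outset, after each block and after each task. It does not place the first PANAS before or after the images. The order of the two blocks is randomised: "Participant will be randomized whether they get meditation first or meditation and TVS first".

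The SAP's Canonical Analysis Strategy starts from the pre-values: "Pre-intervention index values will be interacted with intervention type". If there is no interaction, the post-values are adjusted for the pre-values and intervention type is tested on what remains. No period term is named. The SAP does not say which measurement is the pre-intervention value for the second block.

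**The concern.** Physiology is recorded in calibration, in the blocks and in the tasks, so calibration is the only physiological record made before any intervention. If that record includes or follows a negative-emotion stimulus, it may not be a neutral starting point. The Protocol's own background makes this plausible: section 1.3 cites evidence that inducing positive emotion can "result in faster recovery from cardiovascular sequelae of negative emotions", and HRV during meditation is one of the two primary outcomes.

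Two things are at stake. The first is the quality of the pre-values, which enter the first test the SAP makes. The second is a possible difference between the blocks: any leftover response would fall more on block 1, and nothing in the model absorbs such a difference.

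**Working it through.** **Which pre-values are exposed.** The two orders in section 2.6, side by side:

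- Outline: EEG (with images), pupil, GSR/EKG, vibration.
- A) Calibrations: vibration, GSR/EKG, EEG (with images), pupil.

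Set against the SAP's 13 primary and secondary outcomes:

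- EEG (outcomes 9 to 12, four in all): the images are inside the EEG step, so exposure is possible under either order. No image-free EEG segment is described.
- HRV and GSR (outcomes 2, 6, 7 and 8, four in all): the baseline follows the images under the outline order and precedes them under the other.
- PANAS (outcomes 1 and 3, two in all): timing relative to the images is not stated.

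**Effect on the pre-value by intervention interaction.** Suppose the calibration value serves both blocks. Write it as B = b + c, where b is the person's resting level and c the reaction to the images. B is then common to both conditions and largely cancels in the within-person difference D (TVS plus mindfulness, minus mindfulness alone). The interaction is the slope of D on B. If D depends on b with slope g, and c is unrelated to b and D, the fitted slope is g × var(b) / [var(b) + var(c)], which is smaller than g. If c is related to D, the slope partly measures reactivity to the images. A shift identical in everyone leaves the slope unchanged, so the distortion comes from differences between people. Freedom to stop the images makes such differences in exposure more likely.

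**Effect on a baseline-to-mindfulness change.** If Hypothesis 2.2 is judged by the change from calibration to mindfulness alone, then observed HRV change = true change + r, where r is the amount by which the images had lowered the baseline and which has since recovered. The term r does not cancel, and a true fall smaller than r would be hidden.

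**Effect on the TVS contrast.** The documents give no sample size, alpha, power, effect size or SD, so there is no figure of the plan's to reproduce. All values here are assumptions. Let D = τ + πs + e, with s = +1 if TVS comes first and −1 if second, SD(e) = 1, and two-sided alpha 0.05. Here π is the block 1 shift. A paired test without a period term was compared with a period-adjusted test over 20,000 simulated trials per setting.

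Bias without a period term = π × (n first − n second) / N:

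- 50:50 split: 0 for any π.
- 60:40 split: 0.5 × 0.2 = 0.10 SD; 1.0 × 0.2 = 0.20 SD.

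At a 50:50 split the shift is counted as noise. The expected variance of D becomes 1 + π² × N/(N − 1). For N = 40 that is 1 + 0.25 × 40/39 = 1.256 and 1 + 40/39 = 2.026, so the standard error is inflated by about √1.256 = 1.12 and √2.026 = 1.42.

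Simulated results for N = 40 (power at τ = 0.5):

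| Split | π | Type I error, no period term | Power, no period term | Type I error, period term | Power, period term |
|---|---|---|---|---|---|
| 20:20 | 0 | 0.050 | 0.871 | 0.050 | 0.870 |
| 20:20 | 0.5 | 0.029 | 0.811 | 0.051 | 0.869 |
| 20:20 | 1.0 | 0.006 | 0.614 | 0.050 | 0.869 |
| 24:16 | 0.5 | 0.062 | 0.935 | 0.049 | 0.856 |
| 24:16 | 1.0 | 0.065 | 0.938 | 0.050 | 0.858 |

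The 0.935 and 0.938 are raised by bias in the direction of the effect; with the opposite sign of π or of the imbalance, the bias would work against the effect. For 60:40 splits with π of 0.5 or 1 and N from 20 to 60, type I error without a period term runs from 0.03 to 0.11. With a period term it stays at about 0.05 in every setting.

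**The case against.** The strongest reply is that randomised order already deals with this. A block 1 shift falls on both conditions, and with equal order groups the average TVS effect is unbiased even at a 1 SD shift. That stands for the average contrast. It does not cover precision without a period term, the interaction test or changes from baseline. The allocation ratio and any blocking are not stated, so equal groups cannot be assumed.

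A reader might infer more than the documents support:

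- *That the images come immediately before Intervention 1.* Both lists name at least one step after EEG: three in the outline, one under A).
- *That the baseline and first block do carry a stress response.* The text says only that the images may evoke negative emotions. It gives nothing on their intensity or on how long a response lasts, and the statement in section 1.3 is not about these images.
- *That every physiological model uses the calibration value.* The SAP does not say so for block 2; recordings from the first set of tasks could serve. It also defines no classification for Hypothesis 2.2: its listed moderators are the MAAS, the mDES and meditation frequency.
- *That the pooled contrast mixes a stressed and an unstressed TVS effect.* That needs the TVS effect itself to differ by block, for which there is no evidence. Block 2 follows a block and two tasks, so starting states differ with or without the images.
- *That EEG records will be lost selectively in people with low positive affect.* Nothing links stopping the images to that trait.

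**Conclusion.** The point holds as a possible, unquantified contamination of pre-values. It applies to EEG under either calibration order, to HRV and GSR under the outline order only, and to the PANAS depending on a timing that is not stated. It does not show that the average TVS contrast is biased; that would need unequal order groups and an analysis without a period term.

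The documents give no size. Under the assumptions above, the cost at N = 40 with balanced order is a fall in power from 0.87 to 0.81 or 0.61 for a shift of 0.5 or 1 SD, with a conservative test. With a 60:40 split it is a bias of 0.10 or 0.20 SD. These figures assume a within-person analysis and a shift equal in all participants. They show how the plan would behave if a shift existed, not that one does. A period term repairs this part only; the interaction test and any change from baseline also need clean pre-values.

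**What to change.** - **Protocol, section 2.6:** make the two calibration orders agree. Place the GSR/EKG baseline, a short image-free EEG segment and the initial PANAS before the images, and state the PANAS timing in section 2.5 as well.
- **SAP, Canonical Analysis Strategy:** name these recordings as the pre-intervention values and say how they are used for each block. Add a period term, so that a block 1 shift neither costs precision nor causes bias if the order groups are unequal.
- **Optional:** move the images to the end of the session, but only if they are not needed for EEG set-up. The documents do not say what they are for, so this should not be the default.

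The cost is at most a few minutes of image-free EEG recording and one extra model term. In the illustration, the period term costs almost no power when there is no shift (0.871 against 0.870 at N = 40 with equal groups; 0.872 against 0.857 with a 24:16 split).
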